4.7.1. Primary Endpoints / Variables

All participants are anticipated to have reached the planned end of sequential treatment (EoT) at the time of interim analysis. The primary endpoints of interest for the interim analysis to assess futility and success (as per the iDRC charter) in each arm are:

- 1) The number of participants who have reached 24 weeks after the planned end of sequential treatment (EoT+24wks) and have virological response (VR) at the planned end of treatment (EoT) visit window in the absence of rescue medication.
- 2) The number and proportion of participants achieving SVR (HBsAg < LLOQ and HBV DNA < LLOQ) for 24 weeks after the planned end of treatment (EoT+24wks) in the absence of rescue medication:
 - Arm 1: Week 72 analysis window SVR rate
 - Arm 2: Week 60 analysis window SVR rate
- 3) The number of participants who have not yet reached 24 weeks after the planned end of sequential treatment (EoT+24wks) and have VR at planned end of treatment (EoT) visit window in the absence of rescue medication.
- 4) The number of participants who have not yet reached 24 weeks after the planned end of sequential treatment (EoT+24wks) and have sustained virologic response from planned end of treatment (EoT) to IA data cut-off date in the absence of rescue medication.

4.7.2. Other Endpoints / Variables

The following endpoints, in addition to primary endpoints, will be summarised using descriptive statistics by treatment arm. All of the endpoints below except for 8,13, and 14-21 are also included and defined in the end of study analyses.

- 1) Summary of proportion of participants who achieve HBsAg <LLOQ and HBV DNA <LLOQ over time.

- 2) Summary of proportion of participants who achieve HBsAg <LLOQ and HBV DNA <LLOQ at end of treatment by baseline stratification.
- 3) Summary of proportion of participants who achieved <0.5 , ≥ 0.5 , ≥ 1 , ≥ 1.5 , ≥ 3 log₁₀ IU/mL decline in HBsAg over time by baseline stratification.
- 4) Summary of proportion of participants who achieved <1 , ≥ 1 , ≥ 2 , ≥ 3 log₁₀ IU/mL decline in HBV DNA over time by baseline stratification.
- 5) Summary of actual values and change from baseline over time of HBsAg (log₁₀ IU/mL) and HBV DNA (log₁₀ IU/mL).
- 6) Summary of actual values and change from baseline over time of HBsAg (log₁₀ IU/mL) and HBV DNA (log₁₀ IU/mL) by genotype.
- 7) Summary of HBe antibody (anti-HBeAg) levels over time in HBeAg positive participants.
- 8) Summary of HBe antibody (anti-HBeAg) levels over time in HBeAg positive participants who achieve SVR.
- 9) Summary of actual values and change from baseline over time of HBs antibody (anti-HBsAg).
- 10) Summary of HBs antibody (anti-HBsAg) levels over time.
- 11) Summary of HBs antibody (anti-HBsAg) levels over time in participants who achieve SVR.
- 12) Proportion of participants who achieved ALT normalization with Baseline ALT >ULN over time.
- 13) Summary of proportion of participants who achieved HBV DNA TND over time.
- 14) Summary of concordance of an early virologic response with achieving SVR at PegIFN on-treatment visits Week 6, Week 13, Week 16, Week 20, and Week 24.
- 15) Association between HBV DNA 'Target Not Detected' and relapse in participants who achieve virologic response at end of treatment.
- 16) Summary of ROC analysis for baseline HBsAg as a predictor of SVR in participants who reached end of off-treatment follow-up (EoT+24wks) by IA.
- 17) Summary of baseline characteristics for responders and non-responders.
- 18) Summary of SVR rates for variables potentially associated with response.
- 19) Statistical analysis of variables associated with SVR success - logistic regression – all arms.
- 20) Statistical analysis of variables associated with SVR success - logistic regression – Arm 1 300mg GSK3228836 x24W + PegIFN x24W.
- 21) Statistical analysis of variables associated with SVR success - logistic regression – Arm 2 300mg GSK3228836 x12W + PegIFN x24W.

4.7.3. Statistical Analyses / Methods

An estimation approach with no hypothesis testing will be used to address the primary objective (see Section 4.7.3.1). The analysis will be conducted separately for each arm.

Endpoints / variables specified in Section 4.7.1 and Section 4.7.2 (endpoints 1-13) will be summarised using descriptive statistics, graphically presented (where appropriate), and listed.

Endpoints 14-21 will be analysed as described in Section 4.7.8 as appropriate.

4.7.3.1. Model Specification and Decision Criteria

Predictive probability of meeting SVR thresholds (30 or 35%) will be presented for both arms.

For the posterior probability of SVR rate, with complete data, the number of responders is assumed to follow a Binomial distribution

$$Y \sim \text{Binomial}(N, p)$$

where p is the response rate, with a non-informative prior $\text{Beta}(0.5, 0.5)$, and the posterior distribution for p is

$$\text{Prob}(p|y, N) \sim \text{Beta}(y + 0.5, N - y + 0.5)$$

At the defined time of interim, participants will be at one of two stages in terms of follow-up in the study:

1. **Stage 1:** participants eligible for end of off-treatment follow-up (EoT+24wks) assessment at IA (including participants who have completed at least one visit within their EoT+24wks assessment window and early termination participants who should have completed at least one visit within their EoT+24wks assessment window by the time of the IA data cut).
 - The VR success/failure rate at the end of treatment and SVR success/failure rate at the end of 24-week off-treatment follow-up period (EoT+24wks) will be known for these participants.
 - Participants who fail to achieve VR at end of treatment or fail to sustain a VR from end of treatment (EoT) to the end of follow-up (EoT+24wks), will be classified as SVR failures.
 - Participants achieving SVR at the end of follow-up (EoT+24wks) will be considered SVR successes.
2. **Stage 2:** Participants not yet eligible for end of off-treatment follow-up (EoT+24wks) assessment, i.e., participants between end of treatment (EoT) and EoT+24wks by the time of IA data cut.
 - For these participants, the VR success/failure rate at the end of treatment (EoT) and SVR success/failure rate to the point of IA data cut will be known.
 - Participants who fail to achieve VR at end of treatment (EoT) or fail to sustain a VR from end of treatment (EoT) to the point of IA data cut-off, will be classified as SVR failures.
 - Participants achieving SVR at the time of IA data cut will be considered as potential SVR successes.

Participants who withdraw prior to completing their SVR assessment will be considered as failures. The number of VR/SVR successes for participants at the two stages are summarised in [Table 9](#).

Table 9 Interim Analysis Stages of Follow-Up

	Stage 1: (n.elig)	Stage 2: (n.nelig = N – n.elig)	
	VR Success at EoT	VR Success at EoT and SVR at IA	VR Success at EoT but not SVR at IA
VR Successes	nvr1	nvr2	nvr3
SVR Successes	nSVR1	nSVR2	0
SVR Failures (incl. VR relapse or lost-to-follow-up)	nvr1 – nSVR1	nvr2 – nSVR2	nvr3

EoT = end of treatment; IA = interim analysis; n.elig = eligible for EoT+24wks assessment at IA; n.nelig = not eligible for EoT+24wks assessment at IA; nvr = number of virologic responses; nSVR = number of sustained virologic responses.

For each arm, the predictive probability of meeting the end of off-treatment follow-up (EoT+24wks) success rule is determined from

- nSVR1 (known) out of nvr1, and
- the posterior predictive distribution for nSVR2 out of nvr2+nvr3.

For participants eligible for end of off-treatment follow-up (EoT+24wks) assessment at IA, the SVR success is assumed to follow a binomial distribution

$$Y \sim \text{Binomial}(nvr1, p)$$

where p is the SVR rate, with a non-informative prior Beta (0.5,0.5). If SVR success is obtained, the posterior distribution of p is

$$\text{Prob}(p|nSVR1, nvr1) \sim \text{Beta}(nSVR1 + 0.5, nvr1 - nSVR1 + 0.5)$$

For Stage 2 participants, the predicted number of SVR successes can be obtained from the truncated Beta-Binomial distribution

$$nSVR2 | nSVR1, nvr1, nvr2, nvr3 \sim \text{Beta-Binomial}(nvr2 + nvr3, 0.5 + nSVR1, 0.5 + nvr1 - nSVR1)$$

where nvr2+nvr3 is the total number of participants who were VR successes at EoT but are ineligible for end of off-treatment follow-up assessment at IA. The maximum predicted number of SVR successes (nSVR2) may not exceed the number of participants that have the potential to achieve SVR. Thus, nSVR2 must be in the range [0, nvr2].

The prediction model for the “complete data” number of SVR successes will account for the number of participants who have reached end of treatment (EoT) but not the end of off-treatment follow-up (EoT+24wks) and have failed to either achieve VR or sustain VR. For these participants, it is impossible for them to achieve SVR and must be accounted for in the model.

The predicted number of responders for complete data is $nSVR1 + nSVR2$, where $nSVR2$ is obtained from the truncated Beta-Binomial ($nvr2 + nvr3, 0.5 + nSVR1, 0.5 + nvr1 - nSVR1$) distribution, with the number of predicted additional SVR events ($nSVR2$) being \leq the number of participants with SVR pending.

4.7.3.2. Model Checking and Diagnostics

No model checking is planned for the interim analysis.

4.7.4. Intercurrent Events

Endpoints in Section 4.7.1 and Section 4.7.2 will be summarized regardless of discontinuation of, interruption in, or non-adherence to GSK3228836 or PegIFN treatment unrelated to wide disruptive events (treatment policy strategy). For participants where WDEs on-treatment result in discontinuation of, significant interruption of, and adherence to investigational product (IP), and the participant withdraws from the study, data collected after the intercurrent event will be set to missing and their SVR response will be imputed using all available data for participants for whom SVR can be assessed (hypothetical strategy).

If the participants take rescue medication post-baseline and before/at the assessment of the endpoints, the participants will be considered as non-responders in the interim analysis (composite strategy).

Wide disruptive event includes COVID-19 pandemic related visits. The impact will be captured on COVID-19 eCRF page.

For participants who achieved VR at end of treatment (EoT) and maintained it until the time of IA, but have not reached end of follow-up (EoT+24wks), data for future visits will not be classified as missing. These participants will be classified as potential SVR responders.

Assuming that no rescue medication was taken, missing data at the various stages of the study for endpoints described in Section 4.7.1 will be handled as described below.

4.7.4.1. Missing Primary Data at End of Treatment

End of treatment (EoT) VR response will be determined using the end of treatment analysis window defined in Section 4.2.2.1. If all HBsAg and HBV DNA data within the analysis window for the end of treatment visit is missing and the missingness is not due to wide disruptive events, no imputation of missing data will be performed, and the subject will be considered as a non-responder.

If all HBsAg and HBV DNA data within the analysis window for the EOT visit is missing due to a WDE, and the participant withdraws from the study, the participant will be

classified as not reaching EOT at follow-up. Data after the intercurrent event will be set to missing.

If all HBsAg and HBV DNA data within the analysis window for the EOT visit is missing due to a WDE, but the participant later returns to study and has non-missing data in a later analysis window, the data will be handled in the following two ways:

1. For observed VR responders, the data will be analysed as collected (treatment policy).
2. For observed VR non-responders, data collected after the intercurrent event will be set to missing. The response will be imputed assuming missing at random using all available data from participants for whom SVR can be assessed (hypothetical strategy).

4.7.4.2. Missing Primary Data Post End of Treatment

If all HBsAg and HBV DNA data within an analysis window post the planned end of sequential treatment (EoT) and before/at the assessment is missing not due to wide disruptive events, missing data will be considered as a non-response.

If all HBsAg and HBV DNA data within an analysis window post the planned end of sequential treatment (EoT) and before/at the assessment is missing due to wide disruptive events (such as COVID-19 pandemic) and the participant doesn't have any HBsAg \geq LLOQ or HBV DNA \geq LLOQ or rescue medication at or post planned end of sequential treatment (EoT), the subject will be classified as a potential SVR responder and will be counted among number of participants with VR success at end of treatment (EoT) and maintained until IA (nvr2 in Table 9).

If a participant has any assessments that are affected by a wide disruptive event, but the participant's HBsAg and HBV DNA within an analysis window are collected and the participant is a VR responder, the subject will be classified as a potential SVR responder and will be counted among number of participants with VR success at end of treatment (EoT) and maintained until IA (nvr2 in Table 9).

4.7.4.3. Missing Data for Other Endpoints

In Section 4.7.2, for the proportion of participants in each treatment arm who achieve HBsAg $<$ LLOQ and HBV DNA $<$ LLOQ in the absence of rescue medication at the end of treatment (EoT), the outcome will be determined using the end of treatment analysis window defined in Section 4.2.2.1. In line with the primary endpoint, missing data not due to wide disruptive events will be imputed as a non-response. Missing data due to wide disruptive events will be analysed as collected without any imputation.

Other endpoints will be summarized regardless of completing IP, interruptions in IP or adherence to IP and regardless of rescue medication (except for ALT normalization which can only be achieved in the absence of rescue medication and proportion of participants who achieve HBsAg $<$ LLOQ and HBV DNA $<$ LLOQ). Missing data for these endpoints will be analysed as collected without any imputation. Only available data will be summarized.

HBV DNA, HBsAg, HBeAg levels that are below the LLOQ will be imputed for summaries of actual values and change from baseline following the same rules as in Section 4.1.1.

4.7.5. Subgroup Analyses

Descriptive summaries by baseline strata subgroups defined in Section 4.2.2 will be provided as specified in the OPS. Proportion of participants with HBsAg <LLOQ and HBV DNA <LLOQ at end of treatment will be presented by subgroups defined in Section 4.6.1. No statistical comparison between subgroups will be performed.

4.7.6. Sensitivity Analyses

The analysis using the modified definition of SVR, as detailed in Section 4.7.3.1, will be repeated at the interim analysis.

For the interim analysis, participants who have a value of HBsAg \geq LLOQ or HBV DNA \geq LLOQ at their last visit, which cannot be confirmed due to no further follow up, will be treated as responders/ potential responders as the follow-up is incomplete.

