1. Only for selected sites able to transport to the analysis lab as specified in the SRM

Table 6 PegIFN Dosing for Participants becoming Eligible for PegIFN after Week 1

Become Eligible for PegIFN at PegIFN Eligibility Week (Table 5)	PegIFN Dosing (Table 4) should continue until PegIFN Dosing Week
2	23
3	22
4	21
6	19
8	17
10	15
13	12

Table 7 Off-Treatment Week (OTW) Follow-up: Week 1-24 (Treatment Arm 1) or Week 1-36 (Treatment Arm 2)

Assessments	OTW1 ^a	OTW2	OTW4	OTW8	OTW12	OTW18	OTW24	OTW30 ¹	OTW36 ¹	Early Termination
Window	±3 days									NA
Safety Assessments										
AE/SAE review	X	X	X	X	X	X	X	X	X	X
Concomitant medication review	X	X	X	X	X	X	X	X	X	X
Symptoms directed exam	X	X	X	X	X	X	X	X	X	X
Vital signs	X	X	X	X	X	X	X	X	X	X
Neuropsychiatric assessment (C-SSRS and BDI-II) ²	X		X	X	X		X			X
Laboratory Assessments										
Pregnancy test (WOCBP)	X		X	X	X	X	X	X	X	X
Haematology [includes platelet and WBC with differential]	X		X		X		X			X
PT, INR, aPTT	X		X		X		X			X
Chemistry	X	X	X	X	X	X	X	X	X	X
Urinalysis	X		X		X		X			X
Urine ACR	X		X		X		X			X
HBsAg and HBV DNA	X	X	X	X	X	X	X	X	X	X
Anti-HBsAg and anti-HBeAg	X		X	X	X	X	X	X	X	X
HBeAg (for participants HBeAg positive at screening)	X	X	X	X	X	X	X	X	X	X
Complement C3, C4, C5a, Bb, hs-CRP, MCP-1, ANCA, Ang II	X				X		X			X
PK for PegIFN ²	X	X	X	X						X
HBV RNA and sequencing (HBV genotype/phenotype; HBV DNA and/or RNA)	X	X	X	X	X	X	X	X	X	X
HBcrAg	X		X	X	X		X			X
PBMC Collection for immunophenotyping ³	X						X			X
PAXGene RNA for expression analysis in whole blood	X				X		X			X
Soluble Protein (immunology)	X		X		X		X			X
Archived Samples [serum; plasma]	X	X	X	X	X	X	X	X	X	X

- a. The first planned Off treatment visit occurs 7 days after the planned PegIFN dosing period.
- 1. Only applicable for Treatment Arm 2
- 2. Only for participants that received at least 1 dose of PegIFN.
- 3. Only for selected sites able to transport to the analysis lab as specified in the SRM.

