8.1. Efficacy Assessments

The primary objective measurement for efficacy in this study is the assessment of GSK3228836 treatment followed by PegIFN on serum HBsAg levels in participants with CHB. The primary efficacy endpoint is achieving serum HBsAg level <LLOQ.

Any HBsAg greater than LLOQ after achieving HBsAg seroclearance needs to be confirmed by re-test within 1 week of receiving the test result. The re-test result will be used if the first test is not confirmed.

HBsAg and HBV DNA are collected for primary and secondary efficacy endpoints as per the SoA (see Section 1.3). Details of sample collection can be found in the SRM.

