8.7. Resistance Monitoring

The barrier to development of GSK3228836 resistance is unknown. Population sequencing of isolates from Study ISIS 505358-CS3 did not detect the development of mutations in the GSK3228836 binding site following 4 weeks of GSK3228836 monotherapy.

The risk of resistance development is expected to be lowest in participants receiving concomitant NA therapy due to the suppression of HBV viral replication. Ongoing viral replication during GSK3228836 treatment (e.g., due to virological breakthrough) may increase the risk of the development of resistance. Investigators should therefore consider resistance monitoring for participants who experience virological breakthrough whilst still receiving GSK3228836 (i.e., haven't completed treatment).

Samples collected for viral genotyping and phenotyping may be used for HBV resistance mutation analysis. Viral DNA and/or viral RNA will be extracted from participant samples and the viral genome will be DNA sequenced to determine whether mutations have occurred in the GSK3228836 binding region or elsewhere in the genome (and if applicable, whether any known nucleos(t)ide resistance mutations are present in the polymerase coding region).

Resistance monitoring will be conducted on all baseline isolates to identify pre-existing substitutions. Sequencing of the viral RNA will be attempted in participants receiving stable NA therapy and having low DNA levels (e.g., <LLOQ). Additional resistance monitoring will be conducted and will include, but not limited to, the analysis of isolates from participants experiencing virological failure during or post treatment as defined below. Confirmation of resistance should be done within 1 week after results are received.

Virological breakthrough is defined as one of the following confirmed (2 sequential visits) lab results:

- ≥ 1 log increase from nadir of HBV DNA
- HBV DNA becoming quantifiable after being below the LLOQ

HBsAg levels for each participant will be measured throughout the study. In addition to the standard HBV DNA virological failure criteria defined above, HBV resistance monitoring will also include analysis of isolates from participants with sub-optimal HBsAg levels in the absence of detectable HBV DNA.

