4. STATISTICAL ANALYSES

4.1. General Considerations

All analyses will be performed based on the population of participants with CHB on stable nucleos(t)ide therapy.

The following definitions and abbreviations will be used throughout to define time points for key efficacy endpoints and estimand criteria:

Time point	Definition	Abbreviation
End of treatment	End of sequential treatment of GSK3228836 and Peginterferon. Time point is expected at week 48/36 for Arm 1/Arm 2.	EoT
End of off-treatment follow-up after end of treatment	End of 24 weeks of off-treatment follow-up after end of treatment. Time point is expected at week 72/60 for Arm 1/Arm 2	EoT+24wks
End of study	Final scheduled assessment visit. Time point is expected at week 72 for Arm 1/Arm 2	EoS

The following definitions and abbreviations will be used to define reporting of scheduled efficacy visits:

Time point	Definition	Abbreviation
Scheduled End of GSK3228836 and PegIFN Sequential Treatment	Scheduled visit Week 48 in Arm 1 and Scheduled visit Week 36 in Arm 2.	PegIFN W36/W48
Scheduled End of 24 Weeks after Sequential Treatment	Scheduled visit Week 72 in Arm 1 and Scheduled visit Week 60 in Arm 2.	OT-W24

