4.2.5.1. Using a Modified Definition of SVR

Note for this section: upon review of AIA results, this definition does not meet the scientific intent of the modified definition of SVR. The definition of modified SVR described in this section will be programmed as is. The intended application of this definition will be documented in note to file (NTFs) for this study and for B-clear (209668).

An additional estimand is defined in the same way as the primary estimand, except the population summary is defined using a modified definition of sustained virologic response (SVR) for 24 weeks after the planned end of sequential treatment (EoT) in the absence of rescue medication. The modified definition of SVR is observing HBsAg <LLOQ and HBV DNA <LLOQ at each analysis window in the 24 weeks after the planned end of sequential treatment (EoT). Any observation of HBsAg \geq LLOQ or HBV DNA \geq LLOQ at a visit must be confirmed individually at a consecutive visit (including unscheduled visits or the first visit after the end of the analysis window). If the consecutive visit for the same parameter is also \geq LLOQ, the SVR status for the participant at the initial visit will be an SVR non-responder. If the consecutive visit for the same parameter is also <LLOQ, the SVR status for the participant at the initial visit will be an SVR responder under the modified definition.

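### The interim modified-SVR rule counts an unconfirmed OTW24 rebound as response even when scheduled follow-up has ended, exposing all Arm 1 completers but only some in Arm 2

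*SAP*

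**What the plan says.** Modified SVR is an additional estimand in SAP 4.2.5.1, added to cope with single aberrant laboratory values (SAP 4.8, Table 10). Any HBsAg or HBV DNA value at or above LLOQ "must be confirmed individually at a consecutive visit (including unscheduled visits or the first visit after the end of the analysis window"). If the consecutive value of the same parameter is also at or above LLOQ, "the SVR status for the participant at the initial visit will be an SVR non-responder"; if it is below LLOQ, the participant is a responder. The section opens by conceding that "this definition does not meet the scientific intent of the modified definition of SVR", but keeps the definition for programming and leaves the intended one to notes to file.

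For the interim, SAP 4.7.6 repeats the analysis under this definition. It adds that participants whose last-visit value is at or above LLOQ, "which cannot be confirmed due to no further follow up, will be treated as responders/ potential responders as the follow-up is incomplete". No arm is named, and nothing restricts the rule to participants with visits still to come.

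The off-treatment schedule differs by arm. Protocol Table 7 marks OTW30 and OTW36 as "Only applicable for Treatment Arm 2". SAP 4.1 describes end of study as "Final scheduled assessment visit. Time point is expected at week 72 for Arm 1/Arm 2", which is OTW24 in Arm 1 and OTW36 in Arm 2.

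Protocol 8.1 adds that HBsAg above LLOQ after seroclearance "needs to be confirmed by re-test within 1 week of receiving the test result".

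**The concern.** The reason given in SAP 4.7.6, that follow-up is incomplete, does not fit an Arm 1 participant who has attended OTW24. No scheduled visit remains, and SAP 4.7.3.1 treats the SVR status of participants eligible for the OTW24 assessment as known. Such a participant can have measurable HBsAg or HBV DNA at the endpoint visit and still be counted as a responder.

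This sits awkwardly with the SAP's other interim rules. A completer whose OTW24 window is empty for reasons other than a wide disruptive event is a non-responder (4.7.4.2), and a participant who withdraws before the SVR assessment is a failure (4.7.3.1). A positive value is therefore treated more kindly than no value.

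At stake is a supportive analysis, but one repeated at the interim that informs the Commit to Phase 3 recommendation. How many participants the rule reaches depends on the visit schedule, which differs between arms.

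**Working it through.** **1. The plan's own figure.** The documents give no number for this point. The nearest is the operating characteristic in SAP section 5. With a Beta(0.5, 0.5) prior and n = 50, the smallest y for which 1 − BetaCDF(0.30; y + 0.5, 50 − y + 0.5) exceeds 0.65 is 17. P(Y ≥ 17) at a true rate of 40% is 84.4%; the plan states 84%. It is reproduced and used only in step 5.

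**2. Which values are caught.** HBsAg and HBV DNA are measured at OTW18 and OTW24 in both arms. The exposed pattern is a value below LLOQ before OTW24 and at or above LLOQ at OTW24.
- Arm 1 (SAP Table 2): OTW24 target day 498, window 463 to 518. No scheduled visit follows.
- Arm 2 (SAP Tables 3 and 19): OTW24 target day 414, window 379 to 434. OTW30 has target day 456, which is 456 − 434 = 22 days after the window closes, so OTW30 can be the first visit after the window.

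**3. Exposure at the planned interim.** The cut is 11Oct22 (SAP Table 8). OTW30 falls 456 − 414 = 42 days after OTW24, so an Arm 2 participant needed OTW24 by 30Aug22 to have OTW30 data. Table 8 projects Arm 2 counts at OTW24 of 27 (22Aug22), 45 (03Oct22) and 48 (11Oct22).
- With OTW30: between 27 and 45. Linear interpolation gives 27 + 18 × 8/42 = 30.4.
- Without OTW30: between 48 − 45 = 3 and 48 − 27 = 21, that is 6% to 44% of 48; about 18 by interpolation.
- Arm 1: all of about 18 completers (100%) lack a later scheduled visit.

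These are projected counts and precede any HBsAg re-test.

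**4. Weight of one excused case.** Arm 1: 1/18 = 5.6 percentage points. Arm 2: 1/48 = 2.1 points. In SAP 4.7.3.1 the completers' results also set the Beta-Binomial prediction for participants not yet at OTW24, so an excused completer raises that prediction too. The inputs needed to size this are not given.

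**5. Illustration at full size.** The number of OTW24-only rebounds is an assumption. For one arm of 50 with a true rate of 30%, each excused case is treated as a 2-point rise in the rate. The chance of reaching 17 responders is then:

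| Excused per 50 | P(at least 17) |
|---|---|
| 0 | 31.6% |
| 1 | 43.3% |
| 2 | 55.3% |
| 3 | 66.6% |

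This applies to the final analysis only if unconfirmed OTW24 values are counted as response there.

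**6. Final analysis.** SAP 4.2.5.1 has a branch for a following value at or above LLOQ and a branch for one below. It has none for no following value. The base wording, below LLOQ in every window, points to failure. The modified relapse definition in SAP 4.1.3.2, which requires two consecutive visits, points to no relapse. The case is undefined, and only Arm 2 has a scheduled visit that can resolve it.

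**The case against.** A reader might infer that late relapse is excused in Arm 1 and counted in Arm 2, so that the comparison tilts towards the 24-week regimen. With Beta(0.5, 0.5) posteriors and 50 per arm, responder counts of 14 v 14, 15 v 14 and 16 v 14 (Arm 1 v Arm 2) give Pr(Arm 2 − Arm 1 > −0.05) of 0.714, 0.632 and 0.547. The documents do not support that reading:
- The rule names no arm, and step 3 shows that it also excuses Arm 2 participants at the interim.
- SAP 4.7.3 analyses each arm separately at the interim.
- That probability is specified in SAP 4.3.1.3 for the end-of-study comparison on SVR without a confirmation step, not for modified SVR.
- The final-analysis rule is unstated, so it cannot be said to give the interim result.

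The strongest defence is the protocol 8.1 re-test. It applies in both arms, and SAP 4.2.5.1 accepts unscheduled visits. The Arm 1 window extends 518 − 498 = 20 days past target, so a re-test within 7 days of a result received within 13 days still falls inside it. This stands for HBsAg if the re-test is a new sample, but the documents do not say whether it is a new sample or a re-assay. For HBV DNA, protocol 8.7 says "Virological breakthrough is defined as one of the following confirmed (2 sequential visits) lab results" and asks for resistance to be confirmed within a week, but sets no matching re-test of a rebound.

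A completer may also still be within the OTW24 window at the cut with a repeat pending, because SAP 4.7.3.1 requires only one visit in the window. For that participant the stated reason is fair. Finally, the SAP itself says that the definition misses its intent, and the notes to file were not available.

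**Conclusion.** The point holds as a defect in a supportive analysis. SAP 4.7.6 gives response status to an unconfirmed value at or above LLOQ without checking whether scheduled follow-up is over. All of about 18 Arm 1 completers are exposed, against 3 to 21 of 48 in Arm 2, so the imbalance is one of degree. The clearest exposure is an HBV DNA rebound or a missed HBsAg re-test. The size rests on two things: the projected counts in Table 8, with OTW30 taken on its target day, and the number of OTW24-only rebounds, which is not given and may be zero.

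Primary SVR has no confirmation step (SAP 4.2 and 4.2.2.1) and is untouched. The interim cut of 11Oct22 predates the 22 Mar 2023 approval date listed for SAP v.4.0. The change therefore bears mainly on the final modified-SVR analysis and on how the interim result is reported.

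**What to change.** - In SAP 4.7.6, apply the responder or potential-responder rule only to participants who have not yet reached OTW24.
- In SAP 4.2.5.1 and 4.7.6, state that a value at or above LLOQ at OTW24 is a non-response in both arms unless a repeat of that parameter, HBsAg or HBV DNA, is below LLOQ. Say that an unscheduled visit or the protocol 8.1 re-test counts as the repeat.
- Report an Arm 2 version that does not use OTW30 for confirmation, so that both arms are judged on the same follow-up.
- When reporting the interim modified-SVR result, give the number of participants in each arm counted as responders on an unconfirmed OTW24 value.

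The cost is SAP wording, one derivation and one extra Arm 2 summary. The downside is that a single aberrant OTW24 value with no repeat counts as failure. That works somewhat against the estimand's purpose, but it applies equally to both arms and matches the SAP's non-response handling of missing data unrelated to wide disruptive events.
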